also be reported. Because of the potential for type I errors due to the lack of adjustment for multiple comparisons, the findings for secondary outcomes or sensitivity analyzed should be interpreted as exploratory. All analyses will be performed by using Stata version 14.0.

Safety consideration

Once adverse events occurred during drug intervention, the principal investigator will be informed immediately. Based on the severity of the adverse events and the relation to esketamine, the unmasking process will be considered by the principal investigator. All the adverse events that occurred during the trial will be recorded in detail and closely monitored until stabilization or the time of the study intervention is not the cause for adverse events. All the adverse events will be reported to the Institutional Review Board by the principal investigator.

Patient and public involvement

Patients and the public were not involved in the trial design. Participants will have access to the findings of the study on request.

Ethics and dissemination

This study was approved by the Institutional Review Board of Beijing Tiantan Hospital, Capital Medical University, Beijing, China on October 30, 2020 (KY-2020-058-02). It has been registered on clinicaltrials.gov on June 11, 2020 (NCT04425473). The first participant was recruited on February 19, 2021. The conclusions of this study will be published in peer-reviewed journals.

Discussion

This study is a randomized placebo-controlled double-blinded clinical trial that aims to explore the effect of esketamine on depressive symptoms in the major surgery population. The participants will be administered 0.2 mg/kg esketamine intravenously within 40 min with the suturing of the incision. The efficacy and safety endpoints will be observed during the perioperative period and in the long term after major surgery.

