The null hypothesis of no difference in remission rate between the two arms of intervention will be analysed by a two-sided test at the 5% level of significance.

$$H_0: \lambda_1/\lambda_2 = 1$$

$$H_1: \lambda_1/\lambda_2 \neq 1$$

where λ_1 is the remission rate at postoperative day 3 in the group treated with esketamine and where λ_2 is the same timepoint in the group treated with placebo.

5. Sample size determination

The difference in the remission rates of antidepressant effects between esketamine and ketamine was reported to be 3.8% in patients with treatment-resistant depression. In the perioperative population with depressive symptoms, the remission rate was reported to be 23.1% in the ketamine group and 9.3% in the placebo group on the basis of the PASSION study at our research site. We assumed that the remission rate in the esketamine group would be 19.3% and that in the placebo group would be 10%.

A sample size of 506 participants provided 80% power to show the difference between the esketamine group and the placebo group (with a ratio of 1:1), including 1 interim analysis with a two-sided significance level of 0.05. Considering a 10% attrition rate, the total sample size is planned to be 564.

6. Interim analysis

The planned interim analysis will be performed after 424 patients (75% of the total sample size) have completed the follow-up. This interim analysis is based on the

intention-to-treat principle, and the p value is set at 0.019 following adjustment by the O'Brien-Fleming method. ^[6] The trial will be stopped after interim analysis if a significant difference between the groups is detected.

7. Population analysis

Total population

This population will comprise all the subjects screened and for whom a record exists in the study database. This population will be used for listing adverse events occurring prior to randomization and reasons for withdrawal occurring prior to randomization.

Modified Intent-to-Treat Population

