The intent-to-treat (ITT) population will include all the subjects after randomization and who received esketamine or placebo during surgery. After randomization, it is assumed that all participants have been administered a placebo or esketamine. The modified intent-to-treat population will be excluded from the analysis after randomization situations no longer meet the eligibility criteria, patients who do not have surgery, or patients who cannot undergo follow-up due to surgery-related complications, such as aphasia or coma. The modified ITT population will be tested for demographic characteristics and efficacy and safety outcomes. The population will be used for primary analysis of the efficacy and safety outcomes.

Per-Protocol population

The per protocol (PP) population will comprise all participants except subjects who are confirmed as protocol transgressors. The subjects excluded from the PP population will be confirmed before being blind. This population was used for sensitivity analysis to determine the effect of missing data. In the PP population, subjects will be analysed according to the treatment received and the real events after postoperative assessments.

8. Statistical considerations

The data will be analyzed by Stata 16.0 software (Stata Corp LP, College Station, TX,

USA) and all significance tests will be two-sided, with an alpha setting of 0.05 and 95% confidence intervals confirmed.

Subgroup analysis

The rate of postoperative 3-day remission will be presented at each level of the variables listed below. The degree of change in the treatment effect of each subgroup at different levels will be evaluated via an interaction test.

Multiplicity

The single primary outcome was defined in the protocol, and all other efficacy variables were treated as secondary or other. The only comparison of interest in this study was between esketamine and placebo, and there was no need to adjust for multiple comparisons. All estimates of treatment effects for secondary endpoints will be presented with 95% confidence intervals, no inferential tests will be performed, and only exploratory tests with simple descriptions of these endpoints will be performed.

Missing Data

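### SAP section 7 contradicts itself on who was dosed, no safety set is defined by exposure, and the per-protocol set is given a missing-data purpose it cannot serve

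*SAP*

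**What the plan says.** SAP section 7 (Modified Intent-to-Treat Population) says that the intention-to-treat set "will include all the subjects after randomization and who received esketamine or placebo during surgery". The next sentence reads "After randomization, it is assumed that all participants have been administered a placebo or esketamine". The one after lists the exclusions that give the modified set (m-ITT): patients no longer eligible, patients who had no surgery, and patients who cannot be followed up because of complications such as aphasia or coma. The m-ITT set then carries the primary analysis of both efficacy and safety.

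SAP section 9 (Safety analysis) instead places safety in the total population. Section 7 defines that as everyone screened who has a database record, and gives its use as listing events and withdrawals before randomisation.

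The per-protocol set is everyone except confirmed protocol transgressors, a term that is not defined. Its purpose is stated as follows: "This population was used for sensitivity analysis to determine the effect of missing data". Within it, "subjects will be analysed according to the treatment received" and according to the events actually observed.

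On timing, the Protocol (Randomization and grouping; Intervention and anaesthesia management) has randomisation before surgery and a 40-minute infusion given at suturing.

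**The concern.** A whole operation separates allocation from dosing, so some randomised patients may have surgery and never start the infusion. Section 7 excludes such a patient in one sentence and counts the same patient as dosed in the next. The m-ITT exclusions do not settle the matter, so the primary denominator is open to a choice made after the fact.

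For safety, one candidate set drops patients with coma or aphasia, who are among those whose complications matter most. The other includes people who were never randomised and so belong to no arm. The adverse-event percentages therefore have no single, exposure-based denominator.

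For the per-protocol set, agreement with the m-ITT result could be reported as robustness to missing data when the comparison is mainly about protocol deviations.

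**Working it through.** 1. Apply each rule in the SAP to each kind of patient. Partial receipt is read as receipt, and every patient is taken to have a database record.

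| Patient | ITT sentence | Dosing assumption | m-ITT exclusions | Total population |
|---|---|---|---|---|
| Screened, not randomised | out | not covered | not covered | in |
| Randomised, no surgery | out | counted as dosed | excluded | in |
| Surgery, infusion never started | out | counted as dosed | not named | in |
| Infusion started, not completed | in | counted as dosed | not named | in |
| Infused, then aphasia or coma prevents follow-up | in | counted as dosed | excluded | in |

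The second and third rows show the contradiction, and only the second is resolved by a named exclusion. For safety, the exposed patients are those in the last two rows plus those fully infused without such a complication. Neither candidate set matches that group: m-ITT loses the last row, and the total population adds the first three. Table 2 of the SAP lists infection, bleeding and thrombus, which can be recorded without interviewing the patient, so coma or aphasia is no reason to leave a patient out of those rows.

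2. Per-protocol purpose. A missing-data sensitivity analysis changes what is assumed about unobserved MADRS scores. Removing transgressors changes who is analysed, and no assumption about an unobserved score is varied.

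3. The plan's own sample size. Section 5 states "A sample size of 506 participants provided 80% power to show the difference", "including 1 interim analysis with a two-sided significance level of 0.05". The inputs are 19.3% against 10%, allocated 1:1. The pooled formula is n per arm = [z(0.975)√(2p̄q̄) + z(0.80)√(p₁q₁ + p₂q₂)]² / (p₁ − p₂)², with p̄ = 0.1465. It gives 226 per arm, 452 in total. With a continuity correction the total is 494. With the correction and the final alpha of 0.044 left after 0.019 is used at 75% information, it is 512. The stated 506 lies between the last two, within 3% of each. Attrition: 506 / 0.9 = 562.2, so 563, or 564 as an even total. The figure reproduces and does not depend on the per-protocol or safety set.

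4. Possible size. The documents give no rate of undelivered infusions, so the following shares are assumptions.

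- Patients without a determined place, if the share is the same in both arms: 2% gives 0.02 × 564 = 11.3, and 5% gives 0.05 × 564 = 28.2.
- Power, if a share f of the esketamine arm is never started, stays in that arm and remits at the placebo rate: p₁ = 0.10 + (1 − f) × 0.093. With 253 per arm, two-sided alpha 0.05, the pooled formula and no continuity correction or interim look:

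| f | p₁ | Power |
|---|---|---|
| 0 | 0.1930 | 84.3% |
| 2% | 0.1911 | 83.0% |
| 5% | 0.1884 | 80.9% |
| 10% | 0.1837 | 77.1% |

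The level is above the planned 80% because this formula omits the continuity correction and the interim look, so only the drop is informative: 1.3, 3.4 and 7.2 points. This is the cost of non-delivery if such patients stay in the comparison. It is not a bias created by the wording.

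**The case against.** The strongest reply is that section 7 is loosely worded but the trial captures what is needed. SAP section 9 (Follow-up data) has each centre record intervention details and plans a CONSORT chart, so a reader who inferred that undelivered or stopped infusions would be invisible would be wrong. The gap is in classification and reporting: no rule places an incomplete infusion, and neither Table 1 nor Table 2 has a row for infusion delivery.

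Four other inferences are tempting and not supported.

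- That analysis by treatment received is impossible once receipt is assumed. The sentence assumes one of the two agents, not the assigned one, so regrouping after, say, a syringe mix-up is compatible with it.
- That a patient stopped after a few minutes counts as fully treated in the per-protocol set. No text says so. With transgressor undefined, that patient is unclassified.
- That stopping would fall mainly on esketamine. The Protocol (Safety consideration) says "Once adverse events occurred during drug intervention, the principal investigator will be informed immediately"; it does not mention stopping, and the anaesthesiologists are blinded. Neither document gives a rate by arm.
- That the missing-data question rests on the per-protocol set. The Protocol (Statistical analysis) and SAP section 8 (Missing Data) separately plan sensitivity analyses across imputation methods.

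The per-protocol set might also be defended because it uses observed events, whereas the m-ITT analysis may replace missing assessments with negative results. That contrast does bear on missing data. But it comes from the event rule and not from removing transgressors, and with both changed at once a difference could not be attributed to either.

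The contradiction over dosing, the two unsuitable safety sets and the mislabelled per-protocol purpose remain.

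**Conclusion.** The point holds for stated rules that conflict or do not fit their purpose, and not only for missing detail. The place of a patient who had surgery but never started the infusion is undetermined in the set used for the primary test. Safety has two stated populations, neither based on exposure. The per-protocol set cannot show the effect of missing data by removing transgressors.

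The size is likely to be small. Keeping patients with incomplete infusions in their randomised arm is consistent with an intention-to-treat analysis, and the sample size stands. The only part of the primary analysis left open is the never-started group, whose size the documents do not give; the 2% to 10% shares above are illustrations. No direction of bias between arms can be claimed. The changes are worth making because they are cheap and affect what the safety tables and the per-protocol comparison can be said to show.

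**What to change.** - Delete the sentence that assumes dosing. Reconcile the ITT and m-ITT definitions so that a patient who had surgery but no infusion has one stated place, the same in both arms.
- Define one safety set, all randomised patients whose infusion was started, and use it in sections 7 and 9 in place of the m-ITT set and the total population.
- Restate the per-protocol purpose as the effect of protocol deviations. Define transgressor, including how incomplete infusions count, before unblinding. SAP section 3 already requires membership to be settled by then, but no criteria are given. Any rule that removes incomplete infusions is a post-randomisation exclusion, so the set should remain a sensitivity set.
- Leave missing data to the imputation-based sensitivity analyses already planned in the Protocol and SAP section 8.
- Report infusion delivery by arm (started, completed, not started) from the intervention details that centres already record.
- State that patients with incomplete infusions stay in their randomised arm for the primary test.

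The cost is SAP wording, a few lines in a table and a small change in the safety denominator. The sample size does not change.

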This study is a multicenter randomized controlled clinical trial to explore the effect of esketamine on depressive symptoms screened during the perioperative period (the flow chart see figure 1). It was approved by the Institutional Review Board of Beijing Tiantan Hospital, Capital Medical University, Beijing, China (KY-2020-058-02). All participants or their legal representatives will provide written informed consent after screening and before randomization. Registration information has been supplied on clinicaltrials.gov (NCT04425473).

Participants

The study will be conducted at medical centres in China, and training of the study protocol will be held regularly to guarantee the quality of the trial. Major surgery patients who are 18 to 65 years old with moderate to severe depressive symptoms will be included after informed consent is obtained from their legal representative. Moderate to severe depressive symptoms are defined as Patient Health Questionnaire 9 (PHQ-9)^{18 19} scores equal to or more than 10 and Montgomery-Åsberg Depression Rating Scale (MADRS) scores equal to or more than 22.²⁰ Major surgery is defined as an elective operation with an estimate of more than 2 hours and includes neurosurgical tumour resection, coronary artery bypass grafting operation, total hip or knee arthroplasty surgery, breast cancer surgery, pneumonectomy, or hepatectomy. Patients with any of the following will be excluded: aphasia or other conditions that may lead to the inability for mental assessments; diseases requiring maintenance of intubation after surgery; history of psychotic or bipolar disorder; primary diseases that could change hormone levels with laboratory evidence; body mass index more than 30 kg/m²; Child-Pugh grade B or C (defined as Child-Pugh scores more than 6 points); history of antidepressant therapy in the 2 weeks before screening; repeated suicide attempts (evaluated by a score equal to or more than 3 on the 12-item Quick Inventory of Depressive Symptomatology); history of adverse events to ketamine or esketamine; history of drug use disorder; or current pregnancy or breastfeeding.

Randomization and grouping

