Participants will be randomly assigned to the esketamine group or placebo group at a 1:1 ratio. Randomization results will be achieved via a real-time, online system before surgery. A randomized four-blocks design stratified patients by depressive severity (severe depressive symptoms are defined by MADRS scores equal to or more than 30). The randomization sequence was created by independent engineers who will keep the allocation blind, and all study-related investigators will be blinded to the randomization results.

Intervention and anaesthesia management

All participants included in this study will receive trial drugs intravenously when the incision is being sutured. In the esketamine group, patients will be administered a total dose of 0.2 mg/kg esketamine (Hengrui Induction, Jiangsu, China) over 40 mins. Patients in the placebo group will receive an equivalent volume of normal saline at the same speed. Patients in this study will be under general anaesthesia for major surgery. Anaesthesia management will follow the standard procedure. Total intravenous anaesthesia or balanced anaesthesia will be implemented to maintain appropriate levels of sedation, analgesia, and muscle relaxation. Anaesthetics are administered at appropriate dosages based on consideration of the clinical anaesthetists and will include sedatives (propofol or etomidate), analgesics (sufentanil or remifentanil), muscle relaxants (rocuronium or cisatracurium), or inhaled anaesthetics (sevoflurane). Patient-controlled analgesia devices will be applied after surgery by using sufentanil and ondansetron to maintain numerical rating scale scores equal to or less than 4. Other analgesics could be used with the occurrence of severe pain (numerical rating scale score more than 7) during the postoperative period.

Blinding

The trial drugs will be prepared by an independent person who is not participating in screening, intervention, and follow-up procedures (see figure 2). Esketamine will be diluted to a concentration of 0.5 mg/ml with normal saline. Both esketamine and normal saline will be kept in syringes (50 ml) with the same appearance and labelled with "the trial drugs, randomization code". The participants will receive the trial drug at a speed of 0.6 ml/h per kilogram of weight for 40 min. The intervention will be completed by

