If the amount of missing data is lower than the prescribed attrition rate, which is 10%, the data will drop out. Missing data during the assessment period will be replaced with negative results before breaking blind. Sensitivity analysis will be applied for the different imputation methods, such as imputation with means or medians or dropouts or negative results. The missing data will be reported and analysed to determine their effects on primary efficacy.

9. Statistical analysis

General statistical calculations

For binary outcomes, the summary statistics are reported as the number and proportion, and the χ^2 test was used for hypothesis testing. For outcomes measured on a continuous scale, the summary statistics are reported as the mean and standard deviation (SD) or median and interquartile range (IQR) depending on normality according to the Shapiro-Wilk test. Statistical inference to evaluate the effect of

treatment was presented as absolute mean differences and 95% CIs via the independent t test and linear regression for continuous variables, except skewed variables, for which the absolute difference and 95% CIs were calculated via the Mann-Whitney U test and the Hodges-Lehmann method. All the summarized descriptive statistics will be presented to one further decimal place unless otherwise specified. P values are rounded to 3 decimal places (those less than 0.001 are displayed as <0.001).

Follow-up data

The CONSORT flow chart will be used to summarize the follow-up of patients throughout the trial. Each center records the details of all randomization, intervention, and missing data.

Demographic and baseline characteristics

The demographic information, such as age, sex, weight, height, and body mass index, will be summarized and presented to the participants in the two intervention groups. Other variables included education level, marital status, American Society of Anesthesiologists physical status classification, Charlson's comorbidity index, smoking history, and comorbidity history. Baseline data for operation characteristics, such as delayed extubation, type and extent of resection, and time to spontaneous respiration, will also be obtained.

Efficacy analyses

All statistical analyses for the main effects were two-sided at P values less than 0.05.

Primary efficacy analysis

The primary outcome was postoperative 3-day remission events assessed by the MADRS scale after intervention.

Main Model

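### SAP 7 removes randomised patients from the primary analysis set for lost eligibility without a time limit, so events after the study drug has started could count as grounds for removal

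*SAP*

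**What the plan says.** **Timing.** Under Randomization and grouping, the Protocol states: "Randomization results will be achieved via a real-time, online system before surgery". SAP section 3 repeats this. Under Intervention and anaesthesia management, the Protocol states: "All participants included in this study will receive trial drugs intravenously when the incision is being sutured". The infusion lasts 40 minutes. Eligible operations are expected to exceed 2 hours, so most of the operation lies between allocation and drug.

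**Removal rule.** SAP section 7, Modified Intent-to-Treat Population, says that this set "will be excluded from the analysis after randomization situations no longer meet the eligibility criteria, patients who do not have surgery". The same sentence also removes "patients who cannot undergo follow-up due to surgery-related complications, such as aphasia or coma". SAP section 9, Main Model, runs the primary test in this set.

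**Criteria that surgery could touch.** The Protocol's exclusions under Participants include "aphasia or other conditions that may lead to the inability for mental assessments" and "diseases requiring maintenance of intubation after surgery".

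**Related statements.**
- SAP section 7 also says: "After randomization, it is assumed that all participants have been administered a placebo or esketamine".
- SAP section 3, Planned analyses, fixes the intent-to-treat and per-protocol sets before unblinding. It does not name the m-ITT set.
- SAP section 7 assigns the safety analysis to the m-ITT set; SAP section 9, Safety analysis, assigns it to the total population.
- The Protocol defines no m-ITT set. It mentions the ITT principle only for the interim analysis.

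**The concern.** An eligibility rule normally looks back to a fixed point before treatment. This one refers to patients who have ceased to qualify since randomisation, and it sets no end point. As written, it covers the hours before the infusion and also the recovery period after it.

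A patient who cannot be assessed after surgery, or who stays intubated, could be read as meeting an exclusion criterion and leave the primary set as ineligible. If esketamine changes how often that happens, the arms are no longer compared as randomised. The Protocol's Discussion allows that anaesthetics may act synergistically with esketamine and asks for recovery from anaesthesia to be monitored, so the possibility is not remote from the plan's own thinking.

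Patients removed in this way also leave the denominator altogether and so bypass the missing-data rules in SAP section 8.

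**Working it through.** **1. The plan's own figure.** Inputs from SAP section 5: remission 19.3% against 10%, 80% power, two-sided 0.05, one interim analysis, 10% attrition.
- The continuity-corrected two-proportion formula gives 247 per arm, 494 in total.
- A two-look O'Brien-Fleming inflation at 75% information (factor 1.0195) gives 247 × 1.0195 = 251.8, so 252 per arm and 504 in total, against the stated 506.
- 506 / 0.90 = 562.2, so 563, against the stated 564.

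The sample size reproduces closely and is not in question. It gives 564 / 2 = 282 randomised per arm and an attrition margin of 564 − 506 = 58.

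**2. Grounds for removal, sorted by time.**

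| Ground | When settled | Can the drug influence it? |
|---|---|---|
| Age, scale scores, BMI, Child-Pugh grade, history | Before randomisation | No |
| Operation does not take place | Before the infusion | No |
| New inability to be assessed | Possibly after the infusion | Possibly |
| Prolonged intubation, if read as the exclusion criterion | After the infusion | Possibly |

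Only the last two rows can bias the comparison. The first two cost numbers, provided the decision is blind.

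**3. Size under assumptions.** The documents give no removal frequency. Assume true remission of 10% in both arms among all randomised patients, 282 per arm, and no remission among those removed. Let e1 and e2 be the fractions removed.

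- Observed rates: a = 0.10 / (1 − e1), b = 0.10 / (1 − e2)
- Numbers left: m1 = 282(1 − e1), m2 = 282(1 − e2)
- SE = √[a(1 − a)/m1 + b(1 − b)/m2], shift d = (a − b)/SE
- Two-sided error = P(Z > 1.96 − d) + P(Z < −1.96 − d)

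| e1 | e2 | a | b | SE | d | Error |
|---|---|---|---|---|---|---|
| 5% | 5% | 10.5% | 10.5% | 0.0265 | 0 | 0.050 |
| 2% | 0 | 10.2% | 10.0% | 0.0255 | 0.08 | 0.051 |
| 5% | 0 | 10.5% | 10.0% | 0.0259 | 0.20 | 0.055 |
| 10% | 5% | 11.1% | 10.5% | 0.0272 | 0.21 | 0.055 |
| 10% | 0 | 11.1% | 10.0% | 0.0266 | 0.42 | 0.070 |

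Equal removal produces no spurious difference; the harm depends on the imbalance between arms. These errors are normal approximations for a single nominal 5% test. In the 2% case, an exact binomial calculation shows no inflation.

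**4. Can the trial afford an all-randomised analysis?** Keep all 564 and count the would-be removals as non-remitters, so that both planned rates are multiplied by (1 − x). Power (uncorrected formula, single look, no other losses) is 87.2% at x = 2%, 86.0% at 5% and 83.8% at 10%.

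**5. Internal consistency.** SAP section 7 assumes that every randomised patient received study drug. The next sentence provides for randomised patients who never have surgery. The drug is given at wound closure, so those patients cannot have been dosed. The two statements cannot both hold.

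**The case against.** **The intubation criterion looks forward.** It concerns diseases that require continued intubation, judged in advance, and slow awakening after a study drug is not obviously such a disease. SAP section 9 also lists items "such as delayed extubation, type and extent of resection, and time to spontaneous respiration" as data to be collected, which suggests that these patients stay in. This stands. No passage says that they are removed, and a reader who infers that they will be goes beyond the text. However, the SAP files these items under baseline data although extubation and the return of breathing would ordinarily follow an infusion begun at closure. The plan is thus not strict about what counts as pre-treatment.

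**Membership is fixed blind.** Investigators, anaesthesiologists and assessors are blinded, and analysis sets are settled before unblinding. This prevents selective removal. It does not prevent bias when the drug itself affects the excluding event, and the m-ITT set is not among those named.

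**The effect is small.** On the assumed frequencies this is correct, and the 58-patient margin absorbs modest losses.

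**Two stronger readings are tempting.** One is that randomising before surgery is itself the fault and that allocation should move to wound closure. That would turn cancelled operations into screen failures, but it would leave post-infusion events untouched, and they are the only route to bias. It would also be a substantial change at several centres in a trial that has recruited since February 2021. Randomising before surgery is a legitimate choice. The other is that safety suffers more than efficacy. The documents do not support that: the SAP's two statements on the safety population conflict, and no figure bears on it.

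**Conclusion.** The point holds as a defect in the SAP's definition of the primary analysis set. The eligibility clause is open-ended and so permits removal on post-infusion events; blinding does not cure that if the drug affects them. Removals settled before the infusion and judged blind are not a source of bias.

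The size is unknown and probably small: 10% read as 10.2% to 10.5%, with an error of about 5.1% to 5.5%, for 2% to 5% excess removal in one arm. Those frequencies are assumptions. That no removed patient would have remitted is the least favourable case. The direction depends on which arm loses more patients.

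Two inconsistencies are certain from the text: the dosing assumption against patients without surgery, and the two different safety populations. The change should be made because it is cheap and protects the primary comparison, not because a large bias has been shown.

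**What to change.** Amend the SAP only:

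1. Section 7: limit eligibility-based removal from the m-ITT set to facts dated before the start of the infusion and decided blind. State that events after the infusion starts never make a patient ineligible.
2. Section 3: add the m-ITT set to those fixed before unblinding.
3. Section 9: report removals by arm and reason, and add a sensitivity analysis of all randomised patients. Counting removed patients as non-remitters would match the negative-result option in section 8.
4. Section 7: delete the sentence assuming that all randomised patients were dosed.
5. Sections 7 and 9: reconcile the m-ITT and total-population statements for safety, and name one set.

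The cost is a few sentences and one extra analysis, with no new patients. Patients who become unassessable after the infusion could no longer be removed as ineligible. The separate clause on surgical complications would still reach some of them, and the all-randomised analysis would show how much that matters. The changes should be dated before unblinding.
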